14. FUNDING AND SUPPORT

14.1 Funding

The trial will be conducted by Pharming Technologies B.V.(Sponsor). Pharming will provide IMP to each study site at no cost.

Patients may not be charged for participation or IMP.

15. INSURANCE

In the event of injury to a patient in the study as a result of the study, if the injury:

1. Results from a defect of the manufacturing of rhC1INH (Ruconest®), the patient injuries, to the extent compensable, will be compensated by Pharming or its insurance;
2. Results from the negligence of site personnel in administration of the study, the patient injuries, to the extent compensable, will be compensated by the site or its insurance;
3. Results otherwise from the conduct of the study, the patient injuries, to the extent compensable, will be compensated by the Sponsor or its insurance;

	Short Title:	Ruconest®: Prevention of severe SARS-CoV-2 infection in hospitalized patients with COVID-19	Sponsor: Pharming Technologies B. V.

1 INTRODUCTION

General information on methods and procedures for the statistical evaluation are described in the Study Protocol, Final Version 3.0 dated 12 January 2021. The Statistical Analysis Plan (SAP) presented here outlines the evaluations to be performed in the final statistical analysis, including details with respect to endpoint derivation, applied statistical methods, and presentation of the results.

This Statistical Analysis Plan refers to the final version of the Study Protocol including all approved Amendments by the Version date of the SAP. The SAP will be finalized after the Blind Review of the data and contains a comprehensive and detailed elaboration of the statistical methodology section of the protocol.

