1.3 Data Safety Monitoring Committee

For rhC1INH serious adverse events see the current Investigator's Brochure (IB).

As the frequency of comorbidities in the patient population under study is significant and clinical complications are common in patients with COVID-19 infection, serious adverse events are possible in this setting. Hence, we will establish periodic interim safety review meetings (ISRM) by an independent committee. This Data Safety Monitoring Board (DSMB) will be responsible for safeguarding the interests of the study participants by monitoring adverse events and in particular serious adverse events. The DSMB may also consider factors external to the study when relevant information becomes available, such as scientific or therapeutic developments that may have an impact on the safety of the patients or the ethics of the study. An independent statistician will provide the DSMB with the pertinent safety data. The DSMB's responsibility, roles and procedures will be specified in the study-specific DSMB Charter. A first ISRM will take place after inclusion of 32 patients. The advice(s) of the DSMB will only be sent to Pharming (Sponsor). Should the Sponsor decide not to fully implement this advice, the Sponsor will send the advice to the Institutional Review Board (IRBs) and the Food Drug Administration (FDA), as appropriate, including a note to substantiate why (part of) the advice of the DSMB will not be followed.

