6.2.2 Blinding Procedures

Participants, treating physicians and nurses and Investigators will not be blinded.

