11.4 Planned Analyses

11.4.1 Datasets to be Analysed, Analysis Populations

A review of the database will be conducted in a blinded manner shortly before the database will be locked, and any decisions made at that meeting (blinded Data Review Meeting) concerning the statistical analysis, e.g., additional outcomes and populations, pooling of sites for efficacy analysis, will be documented in the Statistical Analysis Plan (SAP).

Missing data for the primary endpoint will be imputed by means of the Last-observation-carried-forward (LOCF) method, as sensitivity analyses some alternative imputation methods like imputation of the mean and multiple imputation will be additionally performed.

Safety Population: The Safety Population is defined as all patients who received at least one dose of rhC1INH. Statistical analyses will be based on the actual treatment the patient received.

Full Analysis Set/Intent-to-Treat Population: The FAS/ITT Population is defined as all patients who are randomly allocated to a study arm. Statistical analyses will be based on the treatment arm to which the patient was allocated. For quantitative data, the number of patients with non-missing information, means, medians, standard deviations and extremes will be determined. For qualitative data, absolute and relative frequencies will be calculated. Moreover, changes from baseline (V2, d0) will be calculated.

Per Protocol Population: The PP Population is defined as all patients in the FAS/ITT Population who complete the study and who do not have any major protocol violations, including the following:

- Patients who had major inclusion/exclusion criteria violations.

Sufficient compliance is expected because of IV administration of the IMP.

The PP Population will be determined by a blinded review in the Data Review Meeting (DRM) of the data prior to database lock. The primary efficacy analysis will be based on the FAS/ITT Population in this superiority trial; an additional efficacy analysis will be performed on the PP Population. The Safety Population will be used for all safety analyses.

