14.2 Datasets to be analyzed, Analysis populations

A review of the database will be conducted in a blinded manner shortly before the database will be locked, and any decisions made at that meeting (blinded Data Review Meeting) concerning the statistical analysis, *e.g.*, additional outcomes and populations, pooling of sites for efficacy analysis, will be documented in the Statistical Analysis Plan (SAP).

Missing data for the primary endpoint will be imputed by means of the Last-observation-carried-forward (LOCF) method, as sensitivity analyses some alternative imputation methods like imputation of the mean and multiple imputation will be additionally performed.

The following analysis populations will be used for analysis of study data:

Safety population: The Safety Population is defined as all patients who received at least one dose of rhC1-INH. Statistical analyses will be based on the actual treatment the patient received.

Full Analysis Set (FAS)/Intention to treat (ITT) population: The FAS/ITT Population is defined as all patients who are randomly allocated to a study arm. Statistical analyses will be based on the treatment arm to which the patient was allocated. For quantitative data, the number of patients with non-missing information, means, medians, standard deviations and extremes will be determined. For qualitative data, absolute and relative frequencies will be calculated. Moreover, changes from baseline (V2, d0) will be calculated.

Per protocol (PP) population: The PP Population is defined as all patients in the FAS/ITT Population who complete the study and who do not have any major protocol violations, including the following:

- Patients who had major inclusion/exclusion criteria violations.

Sufficient compliance is expected because of IV administration of the IMP.

The PP Population will be determined by a blinded review in the Data Review Meeting (DRM) of the data prior to database lock. The primary efficacy analysis will be based on the FAS/ITT Population in this superiority trial; an additional efficacy analysis will be performed on the PP Population. The Safety Population will be used for all safety analyses.

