14.5.1 Primary efficacy variable

The primary endpoint WHO Ordinal Scale measure at day 7 will be analyzed by means of the nonparametric Wilcoxon rank test stratified by its baseline values with two-sided α -level of 5%. Two adaptive interim analyses after 40 and 80 patients are planned according to the Pocock adjusted levels $\alpha_p = 0.0221$. The results of the sequential groups are combined by the inverse-normal-method (Lehmacher, Wassmer, 1999). There are no prespecified futility margins, but the DSMB can stop the study in the case of insufficient interim results.

Furthermore, 95% confidence intervals will be determined, and the results will be presented graphically by means of box-and-whisker plots.

The analyses will be carried out by the trial biostatistician.

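### The SAP is finalised only after two efficacy interims that compare the arms, leaving additional outcomes and populations, site pooling, per-protocol membership and sensitivity imputations open until just before database lock

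*SAP*

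**What the plan says.** **When the SAP becomes final.** SAP section 1: "The SAP will be finalized after the Blind Review of the data". SAP section 14.2 dates that review: "A review of the database will be conducted in a blinded manner shortly before the database will be locked".

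**What the review may decide.** SAP 14.2 sends to the SAP "any decisions made at that meeting (blinded Data Review Meeting) concerning the statistical analysis". Protocol 11.4.1 has the same rule, with examples: "concerning the statistical analysis, e.g., additional outcomes and populations, pooling of sites for efficacy analysis". Both sections also leave membership of the per-protocol population to this meeting.

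**What comes before it.** Two interim analyses of the primary endpoint are planned, after 40 and 80 patients in SAP 14.5.1 and 14.10, and after 32 and 80 in Protocol 11.4.2 and 11.4.4. Stage results are combined by the inverse-normal method, and the sample size may be changed.

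**Who is blinded, and who analyses.** Protocol 6.2.2: "Participants, treating physicians and nurses and Investigators will not be blinded". SAP 14.5.1, which describes the interims, ends: "The analyses will be carried out by the trial biostatistician". Protocol 1.3 gives the DSMB separate support: "An independent statistician will provide the DSMB with the pertinent safety data".

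**The concern.** A blind review protects the analysis only if those who take part do not know how the arms compare. Here it follows two tests that cannot be run without the allocation, in a trial with no placebo. No section requires a final SAP before an interim. The synopsis gives the only other deadline, which covers the other outcomes of interest and is tied to the database rather than to an interim.

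If the people at the review know the interim trend, an added outcome, an added subgroup of patients, a pooling rule or a sensitivity imputation can be chosen because it agrees with that trend. A reader of the final report could not tell such a choice from one made in ignorance of the results. This matters because the trial, although exploratory, makes a formal two-sided 5% superiority test. Its supportive analyses will be used to judge how robust that test is.

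**Working it through.** **1. The plan's own level.** Inputs: two interims plus a final analysis and overall two-sided α = 0.05 (SAP 14.5.1, 14.8). For three equally spaced looks, solve P(|Z1| > c or |Z2| > c or |Z3| > c) = 0.05, with corr(Zi, Zj) = √(i/j) for i < j. The per-look level is 0.02205, which rounds to the stated 0.0221 (c about 2.29). The plan's figure reproduces and is not in dispute.

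**2. How much has been compared by arm before the SAP is final.**
- First interim: 32/120 = 27% (Protocol) or 40/120 = 33% (SAP).
- Second interim: 80/120 = 67%.
- Correlation of the second-interim statistic with the final one on the planned information scale: √(80/120) = 0.82.

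Anyone who knows the second interim result therefore knows much about the final one.

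**3. What is fixed and what is open.**

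| Element | Status before the review |
|---|---|
| Day-7 WHO score as primary endpoint | Fixed (Protocol 5.1; SAP 5.1.1) |
| Wilcoxon test stratified by baseline score | Fixed (Protocol 11.4.2; SAP 14.5.1) |
| FAS/ITT as primary population; LOCF | Fixed (Protocol 11.4.1, 11.5; SAP 14.2, 14.9) |
| Pocock levels, inverse-normal combination | Fixed (Protocol 11.4.2; SAP 14.5.1) |
| Additional outcomes and populations | Open |
| Pooling of sites for efficacy | Open |
| Per-protocol membership | Open |
| Sensitivity imputations | Two methods given as examples, list not closed |

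The wording that admits any decision on the analysis sets no outer limit.

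**4. Whether the review is masked.** Both documents call it blinded, but neither says how. Doses and dosing times are recorded for the active arm (Protocol 9.2.1). The meeting receives a listing of all protocol deviations (SAP 12), and Protocol 12.4 counts a variation in study-drug dosing as a major deviation. Such an entry would ordinarily point to a patient given rhC1INH, so an unedited listing could reveal the arm.

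**5. Illustrative size.** The documents give neither the number of candidate analyses nor their correlation. Assume two candidates with correlation ρ, the planned test used at both interims, and the better candidate taken at the final look. With three equal stages and c = 2.29, the one-sided error is P(Z1 > c or Z2 > c or max(Z3a, Z3b) > c). Simulation gives:

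| Case | One-sided error |
|---|---|
| Analysis fixed in advance | 2.5% |
| Choice affects stage 3 data only, ρ = 0.9 to 0.7 | about 2.7% to 2.9% |
| Choice affects all stages' data, ρ = 0.9, 0.8, 0.7 | about 2.9%, 3.1%, 3.2% |

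On the two-sided scale with all stages reanalysed, the error is 5.6% to 6.8% for ρ = 0.95 to 0.5, against 5.0%.

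**The case against.** The best defence is that the primary analysis is already settled. Endpoint, test, strata, population, imputation and stopping levels stand in both documents. The review is described as adding outcomes and populations, not replacing them. Protocol changes need IRB approval (Protocol 2.2), and deviations from the planned analyses must be justified and reported (Protocol 11.4.6). This stands, and it confines the exposure mainly to supportive analyses.

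A reader might go further in four ways that the documents do not support:

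- **The primary analysis is not prespecified.** Its core is. Even site pooling leaves the primary p-value unchanged as the plan is written, because the test is stratified by baseline score only and site results are descriptive (SAP 14.7). Pooling would matter to that test only if the meeting altered it.
- **The review is not blind.** Protocol 6.2.2 lists those who are unblinded and does not mention the data reviewers. The supportable criticism is that the method of masking is not stated.
- **The trial biostatistician runs the interims.** The sentence is general and is repeated for the secondary analyses. The dedicated interim sections name no analyst, and DSMB procedures are left to a charter that is not part of these documents. What can be said is that no other analyst is named for efficacy.
- **The error rises to 3.5–4.2%.** That range comes from P(max(Z1, Z2) > 1.96) with correlation 0.9 to 0.7, a single look at one-sided 2.5%. This trial plans three looks at a critical value of about 2.29.

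**Conclusion.** The concern holds as a point about timing and separation of roles. The plan itself places the final SAP after both efficacy interims if the trial runs to plan. It lets the preceding meeting settle analysis questions without stating how that meeting is shielded from interim results. If the trial stops early, fewer than two interims come first.

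The consequence is moderate. The primary test keeps its error rate as long as it is run as written. The figure of about 2.7–3.2% against 2.5% applies only if the meeting were to change that test. It also rests on an assumed two candidates and an assumed correlation of 0.7 to 0.9. The more likely loss is that added outcomes, added populations, the per-protocol result and the sensitivity analyses cannot be presented as chosen without knowledge of the comparison. For an exploratory phase 2a trial this should be corrected, but it does not invalidate the primary analysis.

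**What to change.** 1. Sign and date the SAP before the first interim. Include the full list of outcomes and populations, the rule for pooling sites, the criteria for per-protocol membership and a closed list of sensitivity imputations.
2. Limit the meeting before lock to classifying protocol deviations under those preset rules, on listings without arm or dosing data. Since dosing variations are themselves major deviations, classify them by a written rule so that they need not be judged at the meeting.
3. Extend the role of the independent statistician in Protocol 1.3 to the efficacy interims, and state who may see the results.
4. If an interim has already taken place, record which SAP version existed then and label later choices as post hoc.

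When the SAP is revised, the first interim (32 or 40 patients) and the protocol version it cites (3.0, while the current protocol is 4.0) also need reconciling.

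The cost is an earlier SAP signature. No patients or data are added, and N = 120 and the 0.0221 level stay as they are.

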2 DESIGN OF THE CLINICAL TRIAL

The study is a Phase IIa, randomized, open-label, multi-center, controlled (Standard of care/SOC), parallel group clinical trial of the efficacy and safety of a Ruconest® add-on treatment to SOC conducted in the United States.

It is planned to include a total of approximately 120 patients (80 in experimental and 40 in control group, allocation ratio 2:1).

3 TIME SCHEDULE

The study consists of 7 visits: screening visit (Visit 1, Day -1), and intervention period visits Visit 2 (Day 0), Visit 3 (Day 1), Visit 4 (Day 2), Visit 5 (Day 3-13 during hospital admission), and follow-up visits Visit 6 (Day 14 ± 2 days or discharge) and Visit 7 (Week 4 ± 3 months). A detailed schedule of assessments is presented in the Study Protocol, Final Version 3.0 dated 12 January, 2021 Chapter 9.1.

	Trial Substance:	Ruconest®	Study No.: C1 6201 PROTECT-COVID-19-US
	Short Title:	Ruconest®: Prevention of severe SARS-CoV-2 infection in hospitalized patients with COVID-19	Sponsor: Pharming Technologies B. V.

4 TRIAL OBJECTIVES

Overall Objective

The purpose of this study is to determine whether rhC1-INH administered early during hospital admission for COVID-19 provides additional benefit compared to SOC alone with regards to the clinical course of patients by limiting the local and systemic inflammatory response, and to describe its safety profile in this population.

Primary Objective

The primary objective of the study is to determine if adding 4 days of treatment with rhC1-INH to SOC treatment in adult participants admitted with non-critically ill COVID-19 infection will affect disease severity including progression to severe disease requiring mechanical ventilation within 7 days after enrollment as assessed by the WHO Ordinal Scale for Clinical Improvement.

Secondary Objectives

To evaluate the effect of rhC1-INH treatment in addition to SOC treatment compared to only SOC treatment on disease progression as measured by

Time to clinical improvement (time from randomization to an improvement of two points on the seven-category WHO ordinal scale or live discharge from hospital, whichever came first) within 14 days after enrollment.

Proportion of participants alive and not having required invasive or non-invasive ventilation at 14 days after enrollment.

Proportion of subjects with ARDS (defined by Berlin severity criteria) within 14 days after enrollment.

Safety Objectives

The study aims to assess the safety of rhC1-INH treatment in patients admitted with COVID-19 infection and receiving SOC treatment including overall incidence of adverse and serious adverse events and their relationship to the study treatment during a four-week follow-up.

5 SUBJECTS ASSESSMENTS

5.1 Outcomes

5.1.1 Primary outcome

The primary endpoint will be the disease severity on the 7-point WHO Ordinal Scale on Day 7. This endpoint has been suggested by WHO for clinical trials in patients with COVID-19. The ordinal scale measures illness severity over time.

	Trial Substance:	Ruconest®	Study No.: C1 6201 PROTECT-COVID-19-US
	Short Title:	Ruconest®: Prevention of severe SARS-CoV-2 infection in hospitalized patients with COVID-19	Sponsor: Pharming Technologies B. V.

5.1.2 Secondary outcomes

The secondary endpoints will evaluate the effect of rhC1-INH treatment in addition to SOC treatment relative to only SOC treatment on disease progression as measured by

- Time to clinical improvement (time from randomization to an improvement of two points on the seven-category WHO Ordinal Scale or live discharge from hospital, whichever came first) within 14 days after enrolment.
- Proportion of participants alive and not having required invasive or non-invasive ventilation at 14 days after enrolment.
- Number of days hospitalized (per patient).
- Number of days alive (per patient).
- Proportion of subjects with ARDS (defined by Berlin severity criteria) within 14 days after enrolment.

5.1.3 Other Outcomes of Interest

- Changes on the WHO Ordinal Scale from baseline over 14 days.
- Length of hospital stay until day 28 in survivors.
- Proportion of participants progressing to mechanical ventilation on Day 7 and Day 14.
- Proportion of participants requiring ICU treatment on Day 7 and 14.
- Length of ICU stay until Day 28.
- Ventilator-free days until Day 28.
- All-cause mortality (time from randomization to death within four weeks).
- Changes in biomarker levels until Day 14: CRP, LDH, D-dimer, ferritin, IL-6, lymphocyte count.
- Time to virological clearance of SARS-CoV-2 by PCR from upper or lower respiratory tract samples (time from enrollment to first of 2 negative assays at least 12 hours apart).
- Proportion of patients receiving additional anti-inflammatory treatment such as tocilizumab or immunoglobulins within 14 days.
- Time to defervescence (temperature $<38.0^{\circ}\text{C}$ sustained for at least 48 hours).
- Time to clinical improvement (defervescence, normalization of oxygen saturation ($>93\%$) and respiratory rate) until Day 28.
- Duration of supplemental oxygen until Day 28.

In a subgroup of patients, the pharmacokinetics and pharmacodynamics of rhC1-INH in COVID-19 patients will be characterized by measuring the concentration of rhC1-INH and the activity of C1-INH and inflammatory cytokines and proteins (such as C3, C4).

5.3 Safety variables

The study will evaluate the safety of rhC1-INH in the setting of COVID-19 infections if added to SOC compared to SOC treatment only by measuring the incidence of adverse events up to 3 months post treatment. Moreover, vital signs, physical examinations, and laboratory variables will be assessed for safety.

- Adverse events.
- Physical examination.

	Trial Substance:	Ruconest®	Study No.: C1 6201 PROTECT-COVID-19-US
	Short Title:	Ruconest®: Prevention of severe SARS-CoV-2 infection in hospitalized patients with COVID-19	Sponsor: Pharming Technologies B. V.

A brief, general physical examination will be performed at all visits. Examination will include: height, body weight, eyes, ears/nose/throat, cardiovascular, respiratory, gastrointestinal, genitourinary, musculoskeletal, neurological and psychiatric according to the state of the art.

- Vital signs.

Vital signs will be measured at Visit 2, 3, 4, 5, and 6:

- Heart rate
- Respiratory rate
- Temperature
- Blood pressure (BP_s, BP_d)
- SpO₂.

- Pregnancy.

A serum hCG pregnancy test will be performed at screening in women who may become pregnant, are sexually active, and do not use adequate contraceptive measures.

5.4 Other variables

The following other variables are documented in this clinical trial:

- Demographics and baseline characteristics are to be collected on all patients including age (calculated from year of birth), gender, race, and ethnicity.

Relevant specific medical history will be captured especially the information highlighted below:

- Signs and symptoms (fever, cough, myalgia, headache, sore throat, loss of taste/smell, breathlessness, other).
- Past medical history (diabetes mellitus, hypertension, obesity, cardiovascular diseases, chronic renal diseases, COPD).
- Concomitant medications prior to admission.
- Off label drugs for Covid 19 (Lopinavir/Ritonavir, Hydroxy Chloroquine (HCQ), Remdesivir, other).
- SARS-CoV-2 PCR.
- CT scan chest.

